	
optimum design, there would be a 90.7% chance of detecting a tumor response rate of at least 40% and a response rate of 15% or less would lead to the conclusion that the regimen lacks antitumor activity at a 0.05 significance level. The probability of early stopping (in stage I) is 0.058 if the true response rate of the combination is 40%.
 
Dose Schedule
 
Loading phase: Patients will receive selinexor at 80 mg on D-7 orally. This dose was shown to be tolerable in a study of patients with chronic hematologic malignancies including myeloma (NCT01607892). In addition, patients will receive dexamethasone 40 mg on day -7. The loading phase lasts 1 week.
 
Induction phase: Patients will be treated initially with selinexor at the RP2D PO weekly dose (on days 1, 8, 15) (or twice weekly dosing on cohort 3m and 4m), liposomal doxorubicin at the RP2D IVPB on D1 (at least 2 hours (and no longer than 4 hours) after the selinexor dose), and dexamethasone 40 mg PO weekly (on days 1, 8, 15). Cycles are repeated every 3 weeks (21 days) and patients will receive a maximum of 8 cycles of therapy with this combination. For patients with prior doxorubicin exposure, after a total dose of 450 mg/m^2, patients will be required to have cardiac assessments (echocardiograms or MUGA) every 2 cycles. Any patient with a decrease in ejection fraction of <math>\geq</math> 20% from baseline will have LD discontinued.
 
Maintenance phase: After 8 cycles of therapy with selinexor, LD and dexamethasone, patients will be eligible to proceed on maintenance with the tolerated dose of selinexor and dexamethasone until disease progression. Cycles are repeated every 28 days
 
Discontinuation Criteria:
 
At the discretion of the Investigator, the investigator may remove a patient from the study for the following reasons:
 

• Due to disease progression

• Noncompliance with study procedures

• Patient no longer consents to participate in the study

• Intercurrent illness that interferes with study assessments

• Investigator discretion

• Incidence or severity of AEs in this study indicates a potential health hazard to the patient

• Termination of the study by the sponsor

--	---

	
 
• Pregnancy
 

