
Treatment and Post-Treatment Assessments
	
Loading Phase  Physical examination and vital signs (includes weight and ECOG performance status) (on day -7 only)  Hematology (on day -7 only)  Clinical chemistry (on day -7 only)  Assessment of disease status (Day -7) (SPEP, 24h UPEP, serum free light chain)  PK of selinexor (appendix C)  Adverse events and concomitant medication  Pregnancy test (if applicable)  Bone Marrow aspiration and biopsy at least 2 hours post selinexor dosing on day -7
 
Cycle 1  Physical examination and vital signs (includes weight and ECOG performance status)  Hematology  Complete clinical chemistry (weekly in cycle 1)  Assessment of disease status (SPEP, 24h UPEP, serum free light chain)  PK of doxorubicin, and selinexor and PD (appendix C)  Adverse events and concomitant medication  Pregnancy test (if applicable)
 
Cycle 2 and Beyond  Physical examination and vital signs (on day 1) (includes weight and ECOG performance status)  Cardiac evaluation (echocardiogram or MUGA every 2 cycles if patient has prior anthracycline exposure with greater than 450 mg/m^2)  Hematology (on day 1)  Complete clinical chemistry (on day 1)  Assessment of disease status (SPEP, 24h UPEP, serum free light chain) (on day 1)  Adverse events and concomitant medication  Pregnancy test (if applicable)  PK of doxorubicin, and elinexor and PD (appendix C)
 
Final Visit (end of study)  Physical examination and vital signs (includes weight and ECOG performance status)  Pregnancy test (if applicable)  Cardiac evaluation (echocardiogram or MUGA)  Hematology

--	--

	
Complete clinical chemistry
 
Assessment of disease status (SPEP, 24h UPEP, serum free light chain)
 
Bone marrow aspiration and biopsy (in the event of discontinuation due to disease progression)
 
Adverse events and concomitant medication
 
Pregnancy test (if applicable)

Response	
Response will be assessed per the uniform response criteria of the IMWG incorporating minimal response (<math>\geq 25\%</math> decrease in serum M protein and <math>\geq 50\%</math> decrease in the 24h urine m spike).

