Patients enrolled on cohort 2m will have a 1 week loading phase and selinexor will be administered on days 1,8,15 of the cycle (see below).

Dose level 2m was found to be the recommended phase II dose and will be the dose level used in the phase II / expansion cohort.

MCC 17814 Phase I/II of Selinexor in combination with LD and dexamethasone for Myeloma

Patients enrolled on cohort 3m and 4m will have a 1 week loading phase and receive Selinexor on days 1,3, 8, 10 of the cycle (see below)

After amendment 5, patients will start dosing on dose level 2m

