#### 4.2 Exclusion Criteria

Patients meeting any of the following exclusion criteria are not eligible to enroll in this study.

1. Patients who are pregnant or lactating
2. Radiation, chemotherapy, or immunotherapy or any other approved anticancer therapy  $\leq 2$  weeks prior to day -7 (beginning of loading phase)
3. Major surgery within four weeks before Day -7
4. Myocardial infarct within 6 months before enrollment, New York Heart Association (NYHA) Class II or greater heart failure, uncontrolled angina, severe uncontrolled ventricular arrhythmias, clinically significant pericardial disease, or electrocardiographic evidence of acute ischemic or active conduction system abnormalities
5. Prior cumulative exposure to doxorubicin (including liposomal preparation) > 350mg/m^2
6. Uncontrolled infection requiring parenteral antibiotics, antivirals, or antifungals within one week prior to first dose; patients with controlled infection or on prophylactic antibiotics are permitted in the study;
7. Known to be HIV seropositive;
8. Known active hepatitis A, B, or C infection; or known to be positive for HCV RNA or HBsAg (HBV surface antigen)
9. Any underlying condition that would significantly interfere with the absorption of an oral medication.
10. Grade >2 peripheral neuropathy at baseline.
11. Serious psychiatric or medical conditions that could interfere with treatment
12. Participation in an investigational anti-cancer study within 3 weeks prior to day -7 (beginning of loading phase)
13. Concurrent therapy with approved or investigational anticancer therapeutic. Patients are allowed to receive corticosteroids for the treatment of non-malignant disorders in doses not to exceed the equivalent of prednisone 20 mg/day
14. Patients with coagulation problems and active bleeding in the last month (peptic ulcer, epistaxis, spontaneous bleeding)
15. Patients who have had a previous allogeneic transplant within 6 months and have evidence of clinically significant graft versus host disease.

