## Study Assessment Footnotes

 Prior to the first study-specific measures

 Medical history includes baseline symptoms as well as a detailed history of prior cancer therapies including types and number of prior regimen, refractoriness to immunomodulatory agents and / or proteasome inhibitors, prior anthracycline and total cumulative dose, disease progression during or after therapy, as well as discontinuations due to intolerability or any other serious illness.

 Applicable for women of childbearing potential. Serum  $\beta$ -HCG test within 7 days before the first dose of study drug. To be repeated by urine test, if date of first result exceeds the 7-day window. During cycles 2-8, a pregnancy test is obtained on day 1 of the cycle only.

 Height will be measured at screening only. During cycles 2-8 and maintenance, weight is obtained on day 1 of the cycle only.

 Vital signs: blood pressure, pulse and temperature. During loading, vital signs are obtained on day -7. During cycles 2-8, vital signs are obtained on day 1 of the cycle only. During maintenance, vital signs are obtained on day 1 of the cycle only.

 Full physical examination for baseline and end of study visit. Physical examinations during the study should be symptom directed. During cycles 2-8 and maintenance, physical exam is obtained on day 1 of the cycle only. During loading, physical exam is only on day -7

 Full ophthalmological exam: required at screening and if clinically indicated (change in symptoms develop and especially if there is a baseline cataract or age related macular degeneration). Prior to dilation: best corrected visual acuity, visual field examination via automated perimetry, tonometry, color vision test. Dilated fundoscopy and slit lamp exam

 Echocardiogram or MUGA is required at baseline, at the completion of induction, at discontinuation from the study and as clinically indicated. In addition, in patients who have received a cumulative anthracycline dose >350 mg/m^2, an echocardiogram will be obtained after every 2 cycles of LD.

 Urine analysis will include appearance, color, urine bilirubin, glucose, hemoglobin, ketones, pH, protein, specific gravity, urobilinogen. Microscopy will only be performed if clinically indicated. This will be obtained on screening and as clinically indicated

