### 6.2.2 Treatment Phase

During the treatment phase the following assessments are to be performed:

Physical examination and vital signs	
 
• Body weight
 
• BSA
 
• Blood pressure, pulse, temperature
 
• Physical examination (symptom directed)
 

Cardiac evaluation	12-lead ECG and echocardiogram as clinically indicated. Echocardiogram or MUGA is required at the completion of induction. In addition, in patients who have received a cumulative anthacycline dose >350 mg/m  , an echocardiogram will be obtained after every 2 cycles of LD
Pregnancy test (if applicable)	A serum pregnancy test will be performed in pre-menopausal women and women who are post-menopausal for < 2 years to exclude that a pregnancy occurred under treatment
Hematology	Hemoglobin, white blood cell (WBC) count, absolute neutrophil count and platelet count
Serum chemistry	Sodium, potassium, chloride, bicarbonate, BUN, creatinine, glucose, calcium, phosphate, magnesium, ALT, AST, alkaline phosphatase, total bilirubin, total protein, albumin, LDH
Assessment of disease status	The disease status will be assessed by serum protein electrophoresis, 24h urine for protein electrophoresis and serum free light chain assay on day -14 and every cycle
Adverse events and concomitant medication	Assessed on an ongoing basis
Bone Marrow Biopsy and Aspirate	A bone marrow aspiration and biopsy will be obtained during the loading phase at least 2 hours after the administration of selinexor

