Grade 3 (blistering, ulceration, or swelling interfering with walking or normal daily activities; cannot wear regular clothing) Grade 4 (diffuse or local process causing infectious complications, or a bed ridden state or hospitalization)	Delay dosing up to 2 weeks or until resolved to Grade 0-1. Decrease Liposomal doxorubicin by 1 dose level and return to original dose interval. If after 2 weeks there is no resolution, Liposomal doxorubicin should be discontinued.
Neutropenia	
Grade 1, 2, 3	Maintain dose level. Growth factor support is permitted during the phase II portion and the

	phase I after cycle 1.
Grade 4	Hold study treatment until ANC returns to >800/mm  . Reduce Liposomal doxorubicin by 1 dose level. Recommend growth factor support if not already implemented
Febrile Neutropenia	Hold study treatment until patient has stabilized. Dose reduce LD by 1 dose level and recommended growth factor support
Thrombocytopenia	
Grade 1,2,3 without bleeding	Maintain dose level
Grade 4 or grade 3 with clinical bleeding	Delay study treatment until resolved to thrombocytopenia is resolved to grade 3 or less and bleeding stopped. Reduce LD by 1 dose level. Platelet transfusion are allowed per routine clinical care
Serum Bilirubin (when not related to Gilbert's Syndrome)	
1.2 – 3.0 mg/dL	Reduce LD by 25%
> 3 mg/dL	Reduce LD by 50%
Cardiac Toxicities	
Arrhythmia ≥ grade 2	Hold Liposomal doxorubicin until resolved to ≤ grade 1. Decrease Liposomal doxorubicin by 1 dose level
Arrhythmia ≥ grade 3	Discontinue Liposomal doxorubicin. Patients may continue on selinexor if there is a clinical benefit in the opinion of the investigator
Congestive heart failure ≥ grade 2	Discontinue Liposomal doxorubicin. Patients may continue on selinexor if there is a clinical benefit in the opinion of the investigator
Asymptomatic decrease in ejection fraction by 20% or more	Discontinue Liposomal doxorubicin
Other non-hematologic Adverse Events	
Grade 1, 2	Maintain dose level and initiate standard supportive care
Grade 3	Delay dose until resolved to grade 1 or less, then reduce by 1 dose level
Grade 4	Discontinue Liposomal doxorubicin

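### The synopsis starts two-cycle cardiac scans at 450 mg/m², the calendar and section 6.2.2 above 350 mg/m²; at LD 20 mg/m², following the synopsis omits one to three interim scans in patients entering above 230 mg/m²

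*Combined protocol and SAP*

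**What the plan says.** Four places in the current text set the trigger for an echocardiogram or MUGA every 2 cycles. The quotations stop just before the superscript, so the unit is mg/m² throughout.

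- Synopsis, Dose Schedule, induction phase: "For patients with prior doxorubicin exposure, after a total dose of 450 mg/m".
- Synopsis, Treatment and Post-Treatment Assessments, Cycle 2 and Beyond: "every 2 cycles if patient has prior anthracycline exposure with greater than 450 mg/m".
- Section 5, Study Calendar, footnote 8: "in patients who have received a cumulative anthracycline dose >350 mg/m".
- Section 6.2.2, Treatment Phase, cardiac evaluation: "in patients who have received a cumulative anthacycline dose >350 mg/m".

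Three other provisions bear on the point.

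- Section 4.2, exclusion 5, bars "Prior cumulative exposure to doxorubicin (including liposomal preparation) > 350mg/m".
- Footnote 8 gives everyone a minimum set of scans: "Echocardiogram or MUGA is required at baseline, at the completion of induction, at discontinuation from the study and as clinically indicated".
- Table 3 in section 8.2.4 lists "Asymptomatic decrease in ejection fraction by 20% or more" as a reason to discontinue LD. The synopsis has the same stopping rule.

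Section 6 points the reader to the calendar for an overview. No text says whether the synopsis or the body prevails where they differ.

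**The concern.** The assessment, the interval and the treatment phase are the same in all four places, but the threshold differs by 100 mg/m². The second synopsis line, read literally as exposure before entry, can hardly apply to anyone, because exclusion 5 keeps prior doxorubicin at or below 350 mg/m².

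The threshold matters because it feeds a stopping rule. LD must stop when the ejection fraction falls by 20% or more, even without symptoms. An asymptomatic fall gives the physician no clinical reason to order an extra scan, so in a patient still on induction only the scheduled interim scans would show it. If a site works from the synopsis, patients near the entry cap can go from baseline to the end of induction without one. The trial runs at three centres, so different readings at different sites are a realistic possibility.

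**Working it through.** No stated figure has to be reproduced here. The check counts which interim scans each rule requires.

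**Inputs**

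- LD dose: 20 mg/m² per cycle at dose level 2m. Section 1.5.2 states "Dose level 2m was found to be the recommended phase II dose".
- Maximum LD cycles: 8 (synopsis, Dose Schedule).
- Maximum entry dose: 350 mg/m² (section 4.2, exclusion 5).
- Body threshold: above 350 mg/m² (footnote 8, section 6.2.2).
- Synopsis threshold: 450 mg/m² (Dose Schedule).

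**Assumptions**

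- All 8 cycles are given, without LD dose reduction.
- Interim scans fall after cycles 2, 4 and 6. The cycle 8 scan is the end-of-induction scan that everyone has.
- The total dose in the synopsis means prior plus on-study dose.
- All prior anthracycline is doxorubicin, so one entry dose serves both the entry cap and the trigger.

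**Formula.** With entry dose E, the cumulative dose after cycle k is E + 20k.

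- Body rule, E + 20k > 350: cycle 2 needs E > 350 − 40 = 310; cycle 4 needs E > 350 − 80 = 270; cycle 6 needs E > 350 − 120 = 230.
- Synopsis rule, E + 20k ≥ 450: cycle 2 needs E ≥ 410 and cycle 4 needs E ≥ 370, both above the entry cap; cycle 6 needs E ≥ 450 − 120 = 330.

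| Entry dose (mg/m²) | Interim scans due, above 350 (after cycle) | Interim scans due, 450 (after cycle) | Omitted |
|---|---|---|---|
| up to 230 | none | none | 0 |
| >230 to 270 | 6 | none | 1 |
| >270 to 310 | 4, 6 | none | 2 |
| >310 to <330 | 2, 4, 6 | none | 3 |
| 330 to 350 | 2, 4, 6 | 6 | 2 |

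**Worked case, E = 320.** The cumulative dose is 360 after cycle 2, 400 after cycle 4, 440 after cycle 6 and 480 after cycle 8. The body rule requires scans after cycles 2, 4 and 6. The synopsis rule requires none of them. If the ejection fraction has already fallen by cycle 2, up to six more LD doses (cycles 3 to 8, 6 × 20 = 120 mg/m²) could be given before the end-of-induction scan.

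**Other readings**

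- 450 read as strictly greater than: the last boundary moves from 330 to just above 330; nothing else changes.
- Second synopsis line read as prior exposure only: no one within the doxorubicin cap qualifies, so everyone entering above 310 and up to 350 loses all three scans.
- The 2 cycles counted from the crossing, first scan two cycles later: none omitted up to 250; one for >250 to 290; two for >290 to 330; three for >330 to <350; two at 350.
- The 2 cycles counted from the crossing, first scan at the crossing: the cut-off is above 210, with one to three omitted.
- LD 30 mg/m² (dose level 4m), even cycles: the cut-off is 350 − 180 = 170, with one or two omitted.

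**The case against.** The strongest reply is that the four texts do not exclude one another. The synopsis requires scans from 450 mg/m² and does not forbid earlier ones, so a site that scans above 350 satisfies every line. The calendar and section 6.2.2 are the texts that schedule assessments, they agree, and they are the stricter pair. That is true, and a careful site would follow them. But nothing says that they prevail, and a site reading the synopsis alone would believe it was compliant.

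The size is also conditional. Section 3.2 expects about 3 months of treatment. That is roughly 13 weeks; less one week of loading, it leaves 12 weeks, or four 21-day cycles. A patient who stops after cycle 4 loses nothing in the band from 230 to 270. Above 310 the clear loss is the cycle 2 scan, because the cycle 4 scan falls close to the scan required at discontinuation. The case of six further doses needs a patient near the cap who has a large silent fall by cycle 2 and completes induction. These points limit the size, but the early scan is still lost for patients entering above 310.

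Two further points stand as limits. The body rule counts anthracycline, whereas exclusion 5 caps doxorubicin only, so the bands need not apply to a patient with another prior anthracycline. Eligibility does not require prior anthracycline, at most 47 patients are planned, and the number in the affected bands is unknown. The response endpoint and its decision rules are untouched.

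**Conclusion.** The concern holds. The current text gives two triggers for one safety scan and no rule for choosing between them. At LD 20 mg/m², with 8 cycles and scans after even cycles, following the synopsis Dose Schedule omits one to three interim scans in patients entering above 230 mg/m². Timing the scans from the crossing moves that cut-off to 210 or 250, and LD 30 mg/m² moves it to 170 with one or two scans omitted. Early stopping reduces the loss, sometimes to none. The share of patients affected cannot be computed from the documents. Scans at baseline, at the end of induction, at discontinuation and on clinical indication are unaffected. Because the threshold governs when an asymptomatic ejection-fraction fall would be found and LD stopped, this is more than a clerical slip and should be corrected.

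**What to change.** Change both synopsis lines (Dose Schedule, induction phase; and Cycle 2 and Beyond) so that an echocardiogram or MUGA is done after every 2 cycles of LD once the cumulative anthracycline dose, prior plus on-study LD, exceeds 350 mg/m².

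Use the same sentence in footnote 8 and section 6.2.2. Their threshold stays as it is. The edit there would say explicitly that prior and on-study doses are added, and would name MUGA as an alternative for the interim scan, where they now name only an echocardiogram.

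The essential correction is wording in two synopsis lines; full harmonisation touches all four places. At LD 20 mg/m² under the scan timings above, the practical cost is at most three more scans per affected patient at a site that had followed the synopsis. The calendar and section 6.2.2 already require those scans, and prior cumulative anthracycline dose is already collected at screening.

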## LIST OF ABBREVIATIONS AND DEFINITIONS OF TERMS

AE	Adverse event
ALT (SGPT)	Alanine aminotransferase
AML	Acute myeloid leukemia
ANC	Absolute neutrophil count
AST (SGOT)	Aspartate aminotransferase
AUC	Area under the curve
BMI	Body mass index
BSA	Body surface area
BUN	Blood urea nitrogen
CBC	Complete blood count
CHF	Congestive heart failure
CI	Confidence interval
CNS	Central nervous system
CR	Complete response
CRF	Case report form
CRM1	Chromosome region maintenance protein 1
CTCAE	Common terminology criteria for adverse events
CT Scan	Computed Tomography Scan
CYP450	Cytochrom P450
D	Day
DLT	Dose-limiting toxicity
DNA	Deoxyribonucleic acid
ECG	Electrocardiogram
ECOG	Eastern Cooperative Oncology Group
EOT	End of treatment
GCP	Good Clinical Practice
GI	Gastrointestinal
GLP	Good laboratory practice
H	Hour
HFS	Hand foot syndrome
HR	Hazard ratio
ICH	International Conference on Harmonization
IMWG	International myeloma working group
INR	International normalized ratio
IRB	Institutional review board
ITT	Intent to treat
IV	Intravenous
LDH	Lactate dehydrogenase
m 	Square metre (body surface area)
Mg	Milligram
Min	Minute
MyPRS	Myeloma Prognostic Risk Signature
MCRN	Moffitt Clinical Research Network
MI	Milliliter
MRI	Magnetic resonance imaging
MTD	Maximum tolerated dose

NCI	National Cancer Institute
NES	Nuclear export signal
NYHA	New York Heart Association
ORR	Overall response rate
OS	Overall survival
PD	Pharmacodynamics
PFS	Progression-free survival
PK	Pharmacokinetics
LD	liposomal Doxorubicin
PO	Per oral
PR	Partial response
PTT	Partial thromboplastin time
RP2D	Recommended phase II dose
Topo II	Topoisomerase II
SAE	Serious adverse event
SD	Stable disease
SINE	Selective inhibitor of nuclear export
SUSAR	Suspected unexpected serious adverse reaction
TSH	Thyroid stimulating hormone
TSP	Tumor suppressor protein
TTP	Time to progression
UNL	Upper normal limit
WBC	White blood cell count
XPO1	Exportin 1

## 1 Introduction

### 1.1 Overview

Multiple myeloma accounts for 10% of hematologic malignancies and about 2% of all cancer death in the United States[1]. The United States Food and Drug Administration recently approved 6 agents for the treatment of myeloma including immunomodulators (thalidomide, lenalidomide, pomalidomide), proteasome inhibitors (bortezomib, carfilzomib), and an anthracycline ( liposomal doxorubicin)[2, 4-7, 16, 17]. Despite advances in therapy the disease remains uniformly fatal and finding novel agents to overcome drug resistance represents an unmet medical need.

Cancer cells must inactivate their tumor suppressor proteins (TSPs) in order to perpetuate their neoplastic phenotype. TSPs require nuclear localization in order to function. Like most proteins, TSPs are shuttled into the nucleus by carrier proteins called importins, and they are carried out of the nucleus by exportins. Exportin 1 (XPO1), also called CRM1, is one of seven major nuclear exporters responsible for carrying ~220 cargo proteins out of the nucleus into the cytoplasm[18]. Nearly all TSPs are transported out of the nucleus exclusively by XPO1. Furthermore, XPO1 is overexpressed by 2-4 fold in nearly all cancer cells, and its levels correlate with poor prognosis and/or chemotherapy resistance[19]. Current research suggests that cancer cells have co-opted XPO1 in order to neutralize their TSPs. In addition, DNA topoisomerase II is a substrate for XPO1[19]. Topoisomerase II alpha is located in the cytoplasm of high density myeloma cells consistent with XPO1 activity and lack of response to doxorubicin[14].

Selinexor is a small molecule, drug-like, orally available Selective Inhibitor of Nuclear Export / SINE™ compound that is a slowly reversible covalent antagonist of XPO1. By blocking XPO1, selinexor induces the accumulation of TSPs in the cell nucleus, leading to activation of their tumor suppressing function. Cells with marked genomic (DNA) damage, including cancer cells, undergo apoptotic cell death; normal cells, with little or no genomic damage, undergo transient, reversible cell cycle arrest. Consistent with its novel mechanism of broadly inducing TSP function, selinexor has shown broad anti-tumor in preclinical mouse models and spontaneous canine cancers. Selinexor is currently being studied in three Phase 1 clinical trials in patients with advanced hematologic or solid tumor malignancies, and in patients with treatment refractory sarcomas. Preliminary evidence of anti-tumor activity in humans with a diverse set of cancers formed the basis for studying the effect of selinexor on patients with myeloma. In addition, we have shown that selinexor and other XPO1 inhibitors are able to restore topoisomerase II alpha location into the nucleus and hence susceptibility to doxorubicin, forming the basis of this clinical trial.

